13.5 Protein / Metabolite Statistical Analyses

Primary analyses will be of individual proteins/ metabolites of interest proposed in Aims 1-3. Non-normal levels will be log transformed. Multivariable generalized linear regression adjusted for potential confounders will be used to test for differences in mean values of analytes between HIV+/DD+ and HIV+/DD- subjects. Analytes with >25% values as "0" (e.g. below the lower limits of quantification) will be analyzed as binary traits. Analytes that do not attain normality will be analyzed using non-parametric tests. Benjamini and Hochberg false discovery rate (FDR) will be used for multiple comparisons. To identify novel proteins or metabolites that differentiate HIV+/DD+ and HIV+/DD- subjects, we will analyze all other proteins available on the SomaScan platform and the full array of metabolomic data. FDR will be used for adjustment for multiple comparisons. Box-and-whisker plots will be used to visually assess data, and mean metabolite/protein levels and effect sizes will be compared to those from our previous work in non-HIV cohorts.

SomaLogic's SomaScan platform is a relatively new platform but has been used in many studies including population based studies. There are some existing data that SomaLogic has shared with us including binding specificity for each protein, comparison for some proteins to more standard assays, CVs and lower limits of quantification. For proteins that are found to be significant in this proposal that do not have comparison data to standard assays (and showing high correlation), standard assays (e.g. ELISAs) will also be performed on all samples to validate the results on the SomaLogic platform.

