13.2 Power Calculations and Statistical Analysis for Biomarkers

The primary statistical comparison for Aim 1a is the between group (the HIV+/DD+ and HIV+/DD- cohorts) difference in log-transformed IL-6 biomarker levels. Log-transformed IL-6 (log pg/ml) is expected to have a standard deviation of approximately 0.75.⁵² Sample sizes of 100 subjects in each group will provide 80% and 90% power to detect differences of 0.30 and 0.35 (log pg/ml), respectively. These sample size calculations were based on a two-sample t-test with a two-sided type I error of 0.05. Additionally these calculations suggest that any comparison of (properly transformed) continuous variables between the HIV+/DD- and HIV+/DD+ cohorts will have 80% and 90% power to detect differences of 0.40 and 0.46 standard deviations, respectively. Comparisons between the HIV+/DD+ or HIV+/DD- cohorts and the HIV-/DD+ cohort will have greater power due to the larger number of subjects in the HIV-/DD+ cohort. Statistical summaries will use median (25th, 75th percentiles) and mean (standard deviation) for continuous measures and frequencies (percentages) for categorical variables. Because many biomarkers are expected to be right-skewed, we will log-transform each marker or use another appropriate transformation to normalize its distribution. Unadjusted comparisons between groups will be based on t-tests after the appropriate transformations for continuous measures and chi-square tests for categorical measures. For Aim 1a, propensity scores will be the primary tool used to obtain balanced comparisons between cohorts. The propensity score is defined as the probability of having group membership (e.g. HIV+/DD+) conditional on observed covariates and is a commonly used balancing score used in observational studies.⁵³ Three different methods of propensity score adjustment will be applied. The primary analysis method will be based on inverse probability weightings. Secondary approaches will be based on full propensity score matching and doubly-robust estimation.^{54, 55} Distributional overlap and covariate balance will be assessed using the recently developed best practices for propensity score analyses.⁵⁶ The primary adjusted analysis of IL-6 levels between cohorts will be conducted at the two-sided 0.05 level.

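### Section 13.5 reduces every analyte with more than 25% zeros to detected/not detected; if zeros are non-detects, this costs about 19 to 25 points of avoidable power just above the cut-off and progressively less at heavier censoring.

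*Combined protocol and SAP*

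**What the plan says.** Section 13.5 of the protocol sets three rules for individual proteins and metabolites compared between HIV+/DD+ and HIV+/DD- subjects.

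- Main model: "Multivariable generalized linear regression adjusted for potential confounders will be used to test for differences in mean values of analytes".
- Once more than 25% of an analyte's values are zero, the rule changes: those analytes ("e.g. below the lower limits of quantification) will be analyzed as binary traits").
- The next sentence adds: "Analytes that do not attain normality will be analyzed using non-parametric tests".

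No rank, ordinal or censored-data analysis is named for the second class, even as a sensitivity analysis. The section does not say which rule wins when an analyte has more than 25% zeros and is also non-normal. Multiplicity is handled by the Benjamini-Hochberg false discovery rate, with no level stated.

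The documents give no power for analytes handled as binary. The nearest statement is the general one in section 13.2 for any suitably transformed continuous variable compared between the two HIV+ cohorts, which "will have 80% and 90% power to detect differences of 0.40 and 0.46 standard deviations, respectively".

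**The concern.** A value below the lower limit of quantification is a low level that could not be measured; it is left-censored. At 26% non-detects, 74% of subjects still have a measured level. The binary rule treats all of them as the same value, detected. Ordinal regression with non-detects as the lowest category, or Tobit regression, keeps those levels and accepts the confounder adjustment that section 13.5 asks for.

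What is at stake is missed discoveries. The section scans all remaining SomaScan proteins and the full metabolomic array under FDR control, so the effective threshold for one analyte can be well below 0.05. The section also intends to compare mean levels and effect sizes with earlier non-HIV cohorts, and a detected/not-detected analysis yields no mean difference. The missing precedence rule leaves the choice between a binary and a non-parametric analysis open until the data are seen.

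**Working it through.** **Inputs.** From section 13.2: 100 per group ("Sample sizes of 100 subjects in each group will provide 80% and 90% power"), test and error rate ("based on a two-sample t-test with a two-sided type I error of 0.05"), effect sizes 0.40 and 0.46 SD. From section 13.5: the 25% cut-off. Assumed, because the documents do not give it: the share of non-detects per analyte, taken over 26% to 70%. Also assumed: one normal distribution on the transformed scale, shifted between groups, with a single detection limit; no covariates; complete analyte data.

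**Step 1: reproduce the plan's power.** By the normal approximation, power = Φ(d/√(2/n) − 1.96). For d = 0.40: Φ(2.828 − 1.960) = 80.7%. For d = 0.46: Φ(3.253 − 1.960) = 90.2%. The noncentral t gives 80.4% and 89.9%. The stated 80% and 90% are confirmed.

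**Step 2: binary analysis.** Put the group means at −d/2 and +d/2 with SD 1. Find the limit L from ½Φ(L + d/2) + ½Φ(L − d/2) = c, where c is the pooled share of non-detects. The detected shares are p1 = 1 − Φ(L + d/2) and p2 = 1 − Φ(L − d/2). Power = Φ[(p2 − p1 − 1.96·se0)/se1], with se0 = √(p̄(1 − p̄)·2/n) and se1 = √([p1(1 − p1) + p2(1 − p2)]/n).

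Example, c = 26%, d = 0.40: L = −0.656, p1 = 0.676, p2 = 0.804, difference 0.1282. se0 = √(0.74 × 0.26 × 0.02) = 0.0620 and se1 = 0.0614. Power = Φ[(0.1282 − 0.1216)/0.0614] = Φ(0.108) = 54%.

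**Step 3: analyses that keep the measured levels.** Two were simulated on the same data model: a tie-corrected Wilcoxon test with non-detects tied at the bottom (4,000 or more runs per setting) and a Tobit likelihood-ratio test (500 or 800 runs). The Wilcoxon test stands in for ordinal regression, because without covariates it is the score test of the proportional-odds model.

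Power at 0.40 SD, 100 per group, two-sided 0.05:

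| Non-detects | Detected shares | Binary | Rank | Tobit | Avoidable loss (points) |
|---|---|---|---|---|---|
| 26% | 0.676 / 0.804 | 54% | 76-78% | 79% | 22-25 |
| 30% | 0.631 / 0.769 | 57% | 76% | 79% | 19-22 |
| 40% | 0.523 / 0.677 | 60% | 73-74% | 75% | 12-14 |
| 50% | 0.421 / 0.579 | 61% | 71-72% | 70% | 8-10 |
| 60% | 0.323 / 0.477 | 60% | 66-68% | 68% | 5-8 |
| 70% | 0.231 / 0.369 | 57% | 60% | 60% | about 3 |

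The binary column is the formula in step 2. Simulated binary power agrees to within about 3 points; the largest gap is at 50%, where the discrete test rejects slightly too often (6.0% under no difference). The lower ends of the loss ranges at 50% and 60% use the simulated binary values. Type I error over the settings run was about 5% to 6% for all three methods (largest 6.5%, Tobit at 26%, 800 runs), so the gain is not bought with false positives.

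**Step 4: stricter thresholds.** At alpha 0.001 and 26% non-detects, a 0.60 SD difference is found with 40% power as binary and about 76% by ranks (83% with no censoring). At 0.40 SD the figures are 10%, 26% and 32%.

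**Step 5: zeros that are true absences.** Let the groups differ only in the share of zeros, with identical distributions among the detected. With 36% versus 16% zeros (26% pooled), power is 90% binary and 70% rank. With 60% versus 40%, it is 83% and 75%. The ordering reverses.

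**The case against.** The binary analysis is prespecified and valid. It creates no bias and no excess of false positives, and it can be covariate-adjusted within the generalized linear framework, which a plain rank test cannot. All of that stands: this is a point about efficiency. The primary comparisons of IL-6, fibrosis and left atrial strain have their own analyses and are untouched.

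The text also gives values below quantification only as an example of a zero. If some zeros are true absences, step 5 shows that the binary test can be clearly better. This also stands, and it is why the binary analysis should be kept as a stated option.

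Three stronger readings are tempting but not supported.

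- A reader might infer that every analyte above 25% loses about 20 avoidable points. Only those at about 26-30% non-detects do; the loss declines steadily after that.
- A reader might infer that rank or Tobit analysis costs almost nothing relative to complete data. That is so only near the cut-off. At 50% non-detects these methods are themselves about 9 to 10 points below the uncensored 80%, because censoring has removed that information.
- A reader might take 74% as the share of measured values thrown away. It is the share of subjects with a measured value at 26% non-detects; every one of those values loses its magnitude.

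Finally, the documents do not show how many analytes fall just above 25%, so the practical yield is unknown.

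**Conclusion.** The point holds as a cheap improvement. For an analyte just above the cut-off whose zeros are non-detects, the binary rule lowers power for a 0.40 SD difference from the plan's 80% to about 54-57%, where an analysis that keeps the levels would have about 75-79%. The benefit of changing is moderate up to about 50-60% non-detects and negligible by 70%. Near the cut-off the advantage persists at the stricter threshold of step 4.

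This rests on left-censoring of a single shifted normal distribution, 100 subjects per group with analyte data, and unadjusted tests; the covariate-adjusted ordinal and Tobit models were not themselves simulated. It does not support a claim that binary analysis is always inferior, or that any result from it would be invalid.

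**What to change.** Leave the handling of analytes at or below 25% unchanged. Replace the binary rule in section 13.5, or specify it in the analysis plan that section 13.1 requires before analysis, with wording such as:

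> *Analytes with more than 25% and up to 70% of values below quantification will be compared by covariate-adjusted ordinal (cumulative-logit) regression with non-detects as the lowest category, or by left-censored (Tobit) regression where log-normality is reasonable. Analytes with more than 70% non-detects, or whose zeros represent true absence, will be compared as detected versus not detected. This rule takes precedence over the rule for non-normal analytes.*

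The choice between ordinal and Tobit, and the list of analytes whose zeros mean absence, should be settled before group comparisons are seen.

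Cost: a few sentences and no new data. The ordinal model reports an odds ratio instead of a mean difference. Tobit keeps a mean difference but needs a distributional assumption. Where true absences are not recognised as such, some power is lost compared with the present rule.

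### Section 13.5 dichotomizes any analyte with more than 25% of values below the quantification limit, which loses avoidable power, and states no confounder adjustment for its non-parametric tests

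*Combined protocol and SAP*

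**What the plan says.** All the analysis rules are in section 13.5 (Protein / Metabolite Statistical Analyses).

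- Main model: "Multivariable generalized linear regression adjusted for potential confounders will be used to test for differences in mean values of analytes", comparing HIV+/DD+ with HIV+/DD- subjects.
- Transformation: "Non-normal levels will be log transformed".
- Low-abundance analytes: when more than 25% of values are zero, for example because they are "below the lower limits of quantification) will be analyzed as binary traits".
- Remaining non-normal analytes: "Analytes that do not attain normality will be analyzed using non-parametric tests". No test is named, and covariates are not mentioned.
- Multiplicity: FDR control is mentioned twice, once for the analytes of interest and once for the search across all other proteins and metabolites.

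Section 13.2 gives the power figures. Its general statement covers "any comparison of (properly transformed) continuous variables between the HIV+/DD- and HIV+/DD+ cohorts", and the figures attached to it are 80% power at 0.40 SD and 90% at 0.46 SD. Nothing comparable is given for binary traits or non-parametric tests. Section 13.1 promises a statistical analysis plan before the data are analyzed; no such separate plan is in the text reviewed.

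**The concern.** An analyte with 26% of its values below the limit still has a measured value in 74% of subjects. The binary rule reduces all of those to detected, so a difference in level among detected subjects can no longer contribute. The rule also takes these analytes outside the power statement of section 13.2. The proteomic and metabolomic comparison is a search for new mechanisms (Aim 2c), so power lost here means real markers missed.

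The second issue is adjustment. Section 3.1 links diastolic dysfunction to obesity, hypertension and metabolic syndrome, and links those conditions to raised inflammatory cytokines. The two groups may therefore differ on an analyte for reasons other than diastolic dysfunction. Section 13.5 attaches adjustment to the regression only, and a standard two-sample rank test carries no covariates. FDR control does not repair p-values that are biased by confounding.

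**Working it through.** **Inputs from the documents.** 100 subjects per group, two-sided 0.05, and shifts of 0.40 and 0.46 SD (section 13.2); the 25% threshold (section 13.5).

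**Assumptions, because the documents give no figures.** The analyte is normal on the analysis scale. A pooled share q lies below the limit. A confounder differs by delta SD between the groups and has correlation rho with the analyte.

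**1. The plan's own figure.** Power = Phi(d × sqrt(n/2) − 1.96). For d = 0.40 and n = 100: 0.40 × 7.071 = 2.828, and Phi(0.868) = 80.7%. For d = 0.46 the result is 90.2%. The noncentral t gives 80.4% and 89.9%. The stated 80% and 90% reproduce.

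**2. The binary rule at q = 26%, d = 0.40.** Setting the limit so that 26% of the pooled values fall below it makes the detected shares 0.676 and 0.804, a difference of 0.128.

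- SE under the null: sqrt(2 × 0.74 × 0.26 / 100) = 0.0620.
- SE under the alternative: sqrt((0.676 × 0.324 + 0.804 × 0.196) / 100) = 0.0614.
- Power = Phi((0.1282 − 1.96 × 0.0620) / 0.0614) = 54%.

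As a cross-check, the efficiency of a split at 26% is phi(z)² / (0.26 × 0.74) = 0.547. Power is then Phi(2.828 × sqrt(0.547) − 1.96) = 55%. Reaching 80% with the binary trait would need 183 per group, against 99 for the continuous analysis.

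**3. Methods that keep the measured values.** These were simulated on the same censored data: a Wilcoxon test with values below the limit tied (4,000 runs, standard error under 1 point), and a left-censored (Tobit) likelihood-ratio test (400 runs, standard error about 2 points).

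| Share below limit | Binary (formula) | Binary (simulated) | Wilcoxon with ties | Tobit |
|---|---|---|---|---|
| 26% | 54% | 54% | 76% | 78% |
| 40% | 60% | 61% | 74% | 81% |
| 50% | 61% | 64% | 71% | 74% |
| 60% | 60% | 59% | 64% | 68% |
| 75% | 54% | 53% | 57% | 58% |

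The Tobit value at 40% lies above the one at 26% only through simulation error. A second, separate simulation gave about 55%, 76% and 79% at q = 26%, with null rejection near 5% for all three methods. Its gaps were 6-9 points at 50% and 3-6 points at 75%. At d = 0.46 and q = 26%, the binary test has 66% power, Wilcoxon 88% and Tobit about 90%.

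At 26%, censoring itself therefore costs only a few points from 80%. The other 21-24 points (76 − 55 to 78 − 54) come from dichotomizing.

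**4. If the non-parametric tests were unadjusted.** For an analyte with no relation to diastolic dysfunction, the spurious shift is delta × rho. The rejection rate is the power of the test at that shift, with n scaled by 0.95 for a rank test.

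| delta | rho | Shift (SD) | False-positive rate |
|---|---|---|---|
| 0.2 | 0.1 | 0.02 | 5% |
| 0.3 | 0.3 | 0.09 | 10% |
| 0.5 | 0.3 | 0.15 | 18% |
| 0.5 | 0.5 | 0.25 | 40% |

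For the last row: 0.25 × sqrt(95/2) = 1.72, and 1 − Phi(1.96 − 1.72) is about 40%. A shift of 0.30 SD would give about 54%.

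**The case against.** Several points on the other side stand.

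- **Adjustment is not ruled out.** A reader might infer that the non-parametric tests are unadjusted by design. Section 13.5 does not say so. It names no test, and a binary trait could be fitted by adjusted logistic regression, which is a generalized linear model. The gap is an omission that the promised analysis plan could fill.
- **A single FDR list is not stated.** A reader might infer that adjusted and unadjusted p-values are pooled in one list. FDR is mentioned separately for two sets of analytes, and pooling across types of test is not described.
- **Rank tests are not the source of the power loss.** Their efficiency is about 95% under normality and often higher for skewed data. The loss belongs to the binary rule alone.
- **High false-positive rates are not established.** Any figure depends on an assumed confounding gap, and weak confounding leaves the rate near 5%.
- **Logging of zeros.** A reader might infer that zeros are logged literally in analytes at or below 25%. The text only leaves their handling unstated.
- **Tobit has its own assumption.** It relies on log-normality in the unobserved tail, which a detected/undetected analysis avoids. This is a fair point against using Tobit everywhere, but an ordinal model keeps the ranking of the measured values without that assumption.

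None of this answers the binary rule itself. It is stated outright and, unless changed, would carry forward into the later plan.

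**Conclusion.** The concern holds for the dichotomization rule. For a 0.40 SD shift at two-sided 0.05, the rule gives about 55% power just above its threshold, where methods using the measured values give about 76-79%. The avoidable loss is about 6-10 points at 50% below the limit and about 3-6 points at 75%, so it matters most for analytes that only just cross 25%. These figures assume a normal analyte and no covariates. Absolute power under FDR thresholds would be lower for every method, and the total cost cannot be stated because the share of analytes over 25% is not given.

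On adjustment the conclusion is narrower: section 13.5 states none for the non-parametric tests, and section 3.1 gives reason to want it. The range of about 5% to 40% or more applies only if those tests are run unadjusted and only under the assumed confounding. The documents do not show that the plan commits to confounded tests. Overall this is a worthwhile, low-cost improvement to the analysis.

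**What to change.** In section 13.5, or in the analysis plan before the data are analyzed:

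1. Replace the 25% rule with a covariate-adjusted ordinal (cumulative probability) model that ties all values below the limit at the lowest rank. Left-censored (Tobit) regression on the log scale can be used where log-normality is plausible.
2. Use the same adjusted ordinal model for analytes that do not attain normality.
3. Keep the detected/undetected analysis, fitted as adjusted logistic regression, only for analytes with too few quantified values to support the other models.
4. Define the FDR families and admit only adjusted p-values to each.

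The cost is a change of wording and a little more programming. No additional subjects or assays are needed. The main drawback is Tobit's dependence on log-normality, for which the ordinal model is the fallback.

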13.6 Integrated Molecular Statistical Analysis

Analytic methods will be used for integration of the multi-dimensional data. Principle components analysis (PCA) with varimax rotation and use of the Kaiser criterion for identification of PCA factors will be tested for discrimination. Models will be further tested with random forests and penalized regression,⁶⁷ either with or without dimension reduction.⁶⁸ To control for flexibility, we will test accuracy of prediction with cross-validation. Although high-throughput -omic technologies are used to predict outcomes, they present challenges related to high-dimensional data spaces created where modest number of samples are often defined by

thousands of measurements. We will utilize Bayesian Factor Regression Models^{69,70} to reduce the effective dimension of the data prior to model building. We will utilize a two-step factor regression approach to building predictive models. First, factor models will be used to aggregate subsets of metabolomics or proteomics data into single meta-genes based on high levels of co-expression.⁷¹ Second, the factors will be used collectively as independent variables to build predictive model, either penalized regression or random forests. Model accuracy for discrimination of DD will be assessed by area under the receiver operating characteristic curves. We will also utilize pathway-based models, assessing for over-representation of the most significant predictors in pathways using Ingenuity Software for Pathway Analysis and biochemical pathway analysis using UniPathway annotation (www.grenoble.prabi.fr/obiwarehouse/unipathway).

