5 BASIC STUDY DESIGN

This is a multicenter clinical trial of a cross section of HIV+ patients with and without diastolic dysfunction. Sites currently participating in the Heart Failure Clinical Research Network (HFN) will collaborate with their HIV clinics to identify eligible patients. Approximately 200 HAART-treated virally suppressed HIV+ subjects (100 HIV+/DD+ & 100 HIV+/DD-) will be enrolled. Data will be managed by the HFN Coordinating Center (CC) at Duke University. This study will evaluate biomarkers, phenomapping, metabolomics, cMRI, echocardiography to determine characteristics unique to this patient population. This patient population will then be compared to the MESA (Multi-Ethnic Study of Atherosclerosis) population providing subjects who are HIV-/DD+ (see section 7.0).

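### With about 200 subjects and analytes at platform scale, the Kaiser criterion in section 13.6 keeps nearly every component and no longer separates signal from noise

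*Combined protocol and SAP*

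**What the plan says.** Section 13.6 (Integrated Molecular Statistical Analysis) opens its modelling with PCA and varimax rotation, and says that "use of the Kaiser criterion for identification of PCA factors will be tested for discrimination". No other retention rule and no cap on the number of components is given. The same section describes the general difficulty of -omics work as few samples set against "thousands of measurements".

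Section 5 fixes the sample: "Approximately 200 HAART-treated virally suppressed HIV+ subjects (100 HIV+/DD+ & 100 HIV+/DD-) will be enrolled". Section 13.5 names the contrast ("To identify novel proteins or metabolites that differentiate HIV+/DD+ and HIV+/DD- subjects") and the breadth of the analyte search ("we will analyze all other proteins available on the SomaScan platform and the full array of metabolomic data").

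Section 13.6 also contains safeguards. It says "To control for flexibility, we will test accuracy of prediction with cross-validation", and "Models will be further tested with random forests and penalized regression", where dimension reduction beforehand is optional. It adds a separate Bayesian factor regression step and measures discrimination by area under the ROC curve.

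Three things are not stated: how many analytes enter the PCA, whether they enter pooled or in smaller sets, and whether the PCA is refitted inside each cross-validation fold.

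**The concern.** The Kaiser criterion rests on the idea that an uninformative component has an eigenvalue near 1. That is reasonable when subjects far outnumber variables. When variables far outnumber subjects, the total variance p is squeezed into at most n − 1 non-zero eigenvalues, and noise eigenvalues themselves rise above 1. The threshold then lets everything through.

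Two things are at stake. First, the factors tested for discrimination of diastolic dysfunction would be mostly noise dimensions, which dilutes real signal. Second, varimax would rotate those noise dimensions along with the real ones. This makes the factors hard to read as biological mechanisms, which is the purpose of Aim 2c.

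**Working it through.** Section 13.6 gives no analyte count, component count or AUC target, so there is no figure of the plan's own to reproduce.

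**Inputs**
- n = 200 HIV+ subjects, 100 per group (section 5), so at most 199 non-zero eigenvalues.
- Rule: keep correlation-matrix eigenvalues above 1 (standard meaning of the criterion named in 13.6).
- p, the number of analytes: not in the documents. Assumed range 60 to 5000.
- Correlation structure: not in the documents. Assumed either pure noise or 10 true factors carrying 30% to 85% of each analyte's variance.

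**Step 1: where the noise eigenvalues lie.** For pure noise the smallest non-zero eigenvalue is about (√(p/199) − 1)² (Marchenko–Pastur lower edge).
- p = 400: (1.418 − 1)² = 0.17
- p = 800: (2.005 − 1)² = 1.01
- p = 1000: (2.242 − 1)² = 1.54
- p = 2000: (3.170 − 1)² = 4.71

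From about 800 analytes upward, every noise component passes.

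**Step 2: allowing for correlation.** If a share ψ of each analyte's variance is unique to it, all 199 components pass when ψ(√(p/199) − 1)² > 1, that is, when p > 199(1 + 1/√ψ)².
- Pure noise (ψ = 1): 199 × 4 = 796
- 30% shared (ψ = 0.7): 959
- 50% shared (ψ = 0.5): 199 × 5.83 ≈ 1160
- 70% shared (ψ = 0.3): 199 × 7.98 ≈ 1589
- 85% shared (ψ = 0.15): 199 × 12.83 ≈ 2553

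**Step 3: simulated number of components kept, n = 200** (10 true factors except in the noise column)

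| p | Maximum | Noise | 30% shared | 50% | 70% | 85% |
|---|---|---|---|---|---|---|
| 60 | 60 | 27 | 19 | 11 | 10 | 10 |
| 250 | 199 | 94 | 75 | 54 | 20 | 10 |
| 400 | 199 | 136 | 115 | 88 | 46 | 10 |
| 800 | 199 | 199 | 187 | 165 | 118 | 34 |
| 1000 | 199 | 199 | 199 | 189 | 144 | 56 |
| 1300 | 199 | 199 | 199 | 199 | 181 | 87 |
| 2000 | 199 | 199 | 199 | 199 | 199 | 171 |
| 5000 | 199 | 199 | 199 | 199 | 199 | 199 |

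Repeat runs agreed closely; for example, p = 2000 at 85% shared gave 166 to 171. Parallel analysis on column-permuted data kept exactly 10 components in all 16 settings tried, with p from 1000 to 3000.

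**Step 4: effect on discrimination.** A linear discriminant was fitted to the kept components, with 10-fold cross-validation and the PCA refitted in each fold (12 replicates). Signal, where present, was a 1-SD shift on one factor.

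| p, shared | Signal | Apparent AUC: Kaiser / 10 components | Cross-validated AUC: Kaiser / 10 components |
|---|---|---|---|
| 300, 50% | yes | 0.91 / 0.79 | 0.71 / 0.74 |
| 300, 70% | yes | 0.83 / 0.79 | 0.73 / 0.75 |
| 1300, 50% | no | 1.00 / 0.62 | 0.51 / 0.49 |
| 1300, 50% | yes | 1.00 / 0.78 | 0.69 / 0.73 |
| 1300, 70% | no | 1.00 / 0.63 | 0.49 / 0.51 |
| 1300, 70% | yes | 1.00 / 0.78 | 0.67 / 0.72 |

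The losses in cross-validated AUC are 0.03, 0.02, 0.04 and 0.05. A separate run gave 0.73 − 0.70 = 0.03 at p = 1300 and 0.75 − 0.73 = 0.02 at p = 3000. The apparent AUC of 1.00 at 50% shared is arithmetic: 199 components plus an intercept give 200 parameters for 200 subjects.

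Rotation was not simulated. An orthogonal rotation of standardized scores leaves this unpenalized linear AUC unchanged, so its effect falls on interpretation. With 199 kept and 10 real, 199 − 10 = 189 of the rotated dimensions are noise.

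**The case against.** The strongest reply has four parts.

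**The PCA input is unknown.** The remark about thousands of measurements is general and is not this study's count. The passage in 13.5 on the whole SomaScan platform describes analyte-by-analyte testing with false discovery rate control. If the PCA were run on small pathway sets, the rule could behave well: at p = 60 with at least 50% shared variance it kept 10 or 11 components against 10 true ones. This stands, and it is why the point is conditional on p.

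**Cross-validation is planned.** With the PCA refitted in each fold, the null AUC returns to about 0.5. A reader might infer from the apparent AUC of 1.00 that the study would report perfect discrimination by chance. The documents do not support that: they plan to test predictive accuracy by cross-validation and name no unpenalized classifier. What remains is that refitting within folds is not stated, and that cross-validation does not recover the accuracy lost.

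**Other routes do not depend on the Kaiser count.** Penalized regression and random forests can be run without dimension reduction, and Bayesian factor regression is a separate step. This stands for those routes, but they do not repair the PCA factors that the plan says will be tested. A ridge penalty on standardized, uncorrelated component scores shrinks all coefficients equally and leaves the AUC unchanged (0.69 and 0.67 at p = 1300, as without it). Lasso and random forests on the kept components were not simulated.

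**The analysis is secondary.** Section 13.5 makes individual analytes the primary molecular analysis, and no powered comparison in 13.2, 13.4 or 13.7 uses these factors. This stands.

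**Conclusion.** The point holds conditionally. If about 1000 to 2500 analytes or more enter the PCA, the exact level depending on correlation, the Kaiser criterion keeps nearly all 199 components with about 200 subjects and ceases to select. The cost in simulation is about 0.02 to 0.05 of cross-validated AUC, plus rotated factors that are mostly noise. These figures rest on assumed values of p, factor structure and signal size, and on 12 replicates for the tabulated AUCs.

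Two stronger readings should be resisted. A reader might infer that the rule fails as soon as analytes outnumber the 200 subjects. At p = 250 it keeps from 10 (85% shared) to 94 (pure noise) of 199, so the excess there ranges from none to substantial. A reader might also infer that the PCA step reduces nothing. Thousands of analytes do become at most 199 scores, but that comes from the rank limit and not from the criterion.

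This is a worthwhile, low-cost correction to a hypothesis-generating analysis. No primary comparison is affected.

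**What to change.** In the statistical analysis plan that section 13.1 says will be completed before analysis:

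- State how many analytes enter the PCA and whether platforms are pooled.
- Replace the Kaiser criterion with parallel analysis: keep components whose eigenvalue exceeds the 95th percentile of eigenvalues from column-permuted data. A component count chosen by cross-validation is an acceptable alternative.
- State that standardization, retention and varimax rotation are all carried out inside each cross-validation training fold, and that the cross-validated AUC is the one reported.

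The cost is a few sentences and a little extra computing. No data collection, sample size or primary analysis changes.
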